11.2 Appendix 2: Regulatory, Ethical, and Study Oversight Consideration

Regulatory and Ethical Considerations

- This study will be conducted in accordance with the protocol and with the following:
 - Consensus ethical principles derived from international guidelines including the Declaration of Helsinki and Council for International Organizations of Medical Sciences (CIOMS) International Ethical Guidelines.
 - Applicable International Council for Harmonisation (ICH) Good Clinical Practice (GCP) Guidelines.
 - Applicable laws and regulations.
- The protocol, protocol amendments, ICF, Investigator Brochure, and other relevant documents (e.g. advertisements) must be submitted to an IRB/IEC by the Investigator and reviewed and approved by the IRB/IEC before the study is initiated.
- Any amendments to the protocol will require IRB/IEC and regulatory authority approval, when applicable, before implementation of changes made to the study design, except for changes necessary to eliminate an immediate hazard to patients.
- The Investigator will be responsible for the following:
 - Providing written summaries of the status of the study to the IRB/IEC annually or more frequently in accordance with the requirements, policies, and procedures established by the IRB/IEC.
 - Notifying the IRB/IEC of SAEs or other significant safety findings as required by IRB/IEC procedures.
 - Providing oversight of the conduct of the study at the study center and adherence to requirements of 21 Code of Federal Regulations (CFR), ICH guidelines, the IRB/IEC, EU Clinical Trials Directive 2001/20/EC (if applicable), and all other applicable local regulations.
- After reading the protocol, the Principal Investigator will sign the protocol signature page and send a copy of the signed page to the Sponsor or designee (Section 11.12). The study will not start at any study center at which the Investigator has not signed the protocol.

Adequate Resources

The Investigator is responsible for supervising any individual or party to whom the Investigator delegates study-related duties and functions conducted at the study center.

If the Investigator/institution retains the services of any individual or party to perform study related duties and functions, the Investigator/institution should ensure this individual or party is qualified to perform those study-related duties and functions and should implement procedures to ensure the integrity of the study-related duties and functions performed and any data generated.

Financial Disclosure

Investigators and sub-Investigators will provide the Sponsor with sufficient, accurate financial information as requested to allow the Sponsor to submit complete and accurate financial certification or disclosure statements to the appropriate regulatory authorities. Investigators are responsible for providing information on financial interests during the course of the study and for 1 year after completion of the study.

Insurance

Financial arrangements are detailed in the Investigator Agreement between the Sponsor and Investigator.

The Sponsor will arrange clinical study insurance to compensate patients for any potential injury or death caused by the study.

Informed Consent Process

- The Investigator or his/her representative will explain the nature of the study to the patient and/or the patient's legally authorized representative and answer all questions regarding the study.
- Patients must be informed that their participation is voluntary. Patients will be required to sign a statement of informed consent that meets the requirements of 21 CFR 50, local regulations, ICH guidelines, Health Insurance Portability and Accountability Act (HIPAA) requirements, where applicable, and the IRB/IEC or study center.
- The medical record must include a statement that written informed consent was obtained before the patient was entered in the study and the date the written consent was obtained. The authorized person obtaining the informed consent must also sign the ICF.
- A copy of the original ICF(s) must be provided to the patient or the patient's legally authorized representative.
- ICF New Information: New information since the time of the original consent can be presented to patients in format(s) or method(s) including, but not limited to those listed below unless excluded by local requirements:
 - Revised consent document
 - Addendum to consent

- Memo or other communication to patients
- Orally by phone or in person

Documentation of the method the new information was presented to the patient along with the name of the site staff member and date the new information was presented to the patient must be documented in the patient's source document.

Data Protection

- Patients will be assigned a unique identifier by the Sponsor. Any patient records or datasets that are transferred to the Sponsor will contain the identifier only; patient names or any information which would make the patient identifiable will not be transferred.
- The patient must be informed that his/her personal study-related data will be used by the Sponsor in accordance with local data protection law. The level of disclosure must also be explained to the patient.
- The patient must be informed that his/her medical records may be examined by Clinical Quality Assurance auditors or other authorized personnel appointed by the Sponsor, by appropriate IRB/IEC members, and by inspectors from regulatory authorities.
- The ICF will incorporate (or, in some cases, be accompanied by a separate document incorporating) wording that complies with relevant data protection and privacy legislation.
- The Sponsor/Sponsor's designee will not provide individual genotype results to patients, any insurance company, any employer, their family members, general physician, or any other third party, unless required to do so by law.
- Extra precautions are taken to preserve confidentiality and prevent genetic data being linked to the identity of the patient. In exceptional circumstances, however, certain individuals might see both the genetic data and the personal identifiers of a patient. For example, in case of a medical emergency, the Sponsor or representative physician or an Investigator might know a patient's identity and also have access to his or her genetic data. Also, regulatory authorities may require access to the relevant files.

Administrative Structure

The study administrative structure is in Table 11 and the Medical Monitor and the 24-hour urgent medical contact information is in Table 12.

Table 11: Study Administrative Structure

| Function | Responsible Organization |
|--|-----------------------------|
| Study Operations Management | IQVIA |
| Medical Monitoring | IQVIA |
| Safety Reporting | IQVIA |
| Study Master File | IQVIA |
| Randomization Code | IQVIA |
| Data Management | IQVIA |
| Clinical Supply Management | Verona Pharma plc and IQVIA |
| Quality Assurance Auditing | Verona Pharma plc |
| Biostatistics | Verona Pharma plc and IQVIA |
| Medical Writing | Verona Pharma plc and IQVIA |
| Laboratory Assessments | Q2 Solutions and IQVIA |
| Electrocardiogram Collection, Review, and Analysis | eResearch Technology (ERT) |

Table 12: Medical Monitor

| | | |
|------------|------------|------------|
| [REDACTED] | [REDACTED] | [REDACTED] |
| [REDACTED] | [REDACTED] | [REDACTED] |
| [REDACTED] | [REDACTED] | [REDACTED] |

Dissemination of Clinical Study Data

For studies conducted in the United States, the results of the study are required to be reported on clinicaltrials.gov no later than 1-year after the primary completion date of the clinical study, which is defined as the date of final data collection for the primary outcome measure.

Data Quality Assurance

- All patient data relating to the study will be recorded on printed or eCRFs unless transmitted to the Sponsor or designee electronically (e.g. laboratory data). The Investigator is responsible for verifying that data entries are accurate and correct and will need to confirm that the blinding procedures have or have not been maintained for each patient by physically or electronically signing the eCRF.
- The Investigator must maintain accurate documentation (source data) that supports the information entered in the eCRF.
- The Investigator must permit study-related monitoring, audits, IRB/IEC review, and regulatory agency inspections and provide direct access to source data documents.
- The Sponsor or designee is responsible for the data management of this study including quality checking of the data.
- Study monitors will perform ongoing source data verification to confirm that data entered into the eCRF by authorized study center personnel are accurate, complete, and verifiable from source documents; that the safety and rights of patients are being protected; and that the study is being conducted in accordance with the currently approved protocol and any other study agreements, ICH GCP, and all applicable regulatory requirements.
- Records and documents, including signed ICFs, pertaining to the conduct of this study must be retained by the Investigator for 15 years after study completion unless local regulations or institutional policies require a longer retention period. No records may be destroyed during the retention period without the written approval of the Sponsor. No records may be transferred to another location or party without written notification to the Sponsor.

Source Documents

The Investigator/institution should maintain adequate and accurate source documents and study records that include all pertinent observations on each of the study center's patients. Source data should be attributable, legible, contemporaneous, original, accurate, and complete. Changes to source data should be traceable, should not obscure the original entry, and should be explained if necessary (e.g. via an audit trail).

- Source documents provide evidence for the existence of the patient and substantiate the integrity of the data collected. Source documents are filed at the Investigator's study center.
- Data reported on the eCRF or entered in the eCRF that are transcribed from source documents must be consistent with the source documents or the discrepancies must be explained. The Investigator may need to request previous medical records or transfer records, depending on the study. Also, current medical records must be available.
- Definition of what constitutes source data can be found in ICH E6(R2) Section 1.51.

Study and Study Center Closure

The Sponsor reserves the right to close the study center or terminate the study at any time for any reason at the sole discretion of the Sponsor. Study centers will be closed upon study completion. A study center is considered closed when all required documents and study supplies have been collected and a study center closure visit has been performed.

The Investigator may initiate study center closure at any time, provided there is reasonable cause and sufficient notice is given in advance of the intended termination.

Reasons for the early closure of a study center by the Sponsor or Investigator may include but are not limited to:

- Failure of the Investigator to comply with the protocol, the requirements of the IRB/IEC or local health authorities, the Sponsor's procedures, or GCP guidelines.
- Inadequate recruitment of patients by the Investigator.
- Discontinuation of further study medication development.

Publication Policy

The data generated by this study are confidential information of the Sponsor.

11.3 Appendix 3: Clinical Laboratory Tests

The tests detailed in Table 13 will be performed by the central laboratory.

- Fasting is not required prior to laboratory testing.
- Laboratory tests should be collected prior to dosing with blinded study medication.

Table 13: Protocol Required Safety Laboratory Assessments

| Chemistry | Hematology | Viral Serology |
|---|------------------------------|--|
| Albumin | Hemoglobin | Hepatitis B Serology (Markers include HBsAg, anti-HBs, anti-HBc, and others) |
| Alkaline phosphatase | Hematocrit | Hepatitis C virus antibody |
| Alanine amino transferase (ALT or SGPT) | Platelet count | |
| Aspartate amino transferase (AST or SGOT) | WBC count | Other |
| Bilirubin, direct | Leukocyte differential count | Pregnancy test for Women ¹ |
| Bilirubin, indirect | Neutrophils, absolute | COVID-19 testing ² |
| Bilirubin, total | Neutrophils, segs (%) | |
| Calcium | Neutrophils, bands (%) | Biomarkers |
| Chloride | Basophils (%) | IL-6 |
| CO2 content/Bicarbonate | Eosinophils (%) | IL-8 |
| Creatinine | Eosinophils, absolute | C-Reactive Protein (CRP) |
| Creatine phosphokinase (CPK), total | Lymphocytes (%) | |
| Gamma glutamyl transferase (GGT) | Monocytes (%) | Genotyping |
| Glucose | RBC count | CYP2C9 |
| Phosphorus | | CYP2D6 |
| Potassium | | |
| Protein, total serum | | |
| Sodium | | |
| Urea nitrogen (BUN) | | |
| Uric Acid | | |
| 
¹ Pregnancy test for women of childbearing potential. Serum pregnancy test will be conducted at visits where Chemistry and Hematology are performed. Urine pregnancy test will be conducted at Visit 1 and visits where no other central laboratory testing is being conducted.
 
² COVID-19 test (optional) may be performed locally.
 
Abbreviations: CYP=cytochrome P450; CYP2C9=CYP isoenzyme 2C9; CYP2D6=CYP isoenzyme 2D6; HBsAg= hepatitis B surface antigen; anti-HBs= hepatitis B surface antibody; anti-HBc=total hepatitis B core antibody; IL=interleukin.
 | | |

Additional Instructions:

- The Investigator must review the laboratory report, document this review, and record any clinically relevant changes occurring during the study in the AE section of the eCRF.
- If additional tests (Except COVID-19 test) are required to be completed urgently by a local lab to assess an adverse event or for any other reason, these labs should also be

completed by the central laboratory for this study using the unscheduled laboratory forms and procedures provided in the laboratory manual. The values obtained by the central laboratory will override the values obtained by the local laboratory.

- COVID-19 test may be performed locally.
- The laboratory reports must be signed by the investigator who reviewed the report and filed with the source documents.
- Clinically significant abnormal laboratory findings are those that are not associated with the patient's healthy status and judged by the Investigator to be more severe than expected.
- All laboratory tests with values considered clinically significantly abnormal after randomization should be repeated until the values return to normal or baseline or are no longer considered clinically significant by the Investigator or Medical Monitor.
 - If such values do not return to normal/baseline within a period of time judged reasonable by the Investigator, the etiology should be identified, and the Sponsor notified.
 - All protocol-required laboratory assessments must be conducted in accordance with the laboratory manual that will be developed by the central laboratory vendor and per the timelines outlined in the SoA (Section 1.3).
 - If laboratory values from non-protocol specified laboratory assessments performed at the institution's local laboratory require a change in patient management or are considered clinically significant by the Investigator (e.g. SAE or AE), then the results must be recorded in the eCRF.

11.4 Appendix 4: ECG Exclusion Criteria

A 12-lead ECG recording at Screening showing any of the following abnormalities:

- Sinus tachycardia ≥ 110 bpm (Sinus tachycardia ≥ 110 bpm should be confirmed by 2 additional readings at least 5 minutes apart.).
- Sinus bradycardia < 45 bpm (Sinus bradycardia < 45 bpm should be confirmed by 2 additional readings at least 5 minutes apart).
- Multifocal atrial tachycardia
- Junctional (heart rate > 100 bpm)
- Supraventricular tachycardia (> 100 bpm)
- Ventricular tachycardia
- Atrial fibrillation with rapid ventricular response (rate > 100 bpm).
- Atrial flutter
- Frequent VPCs (> 2 on a 10 sec ECG)
- Ventricular flutter
- Ventricular fibrillation
- Torsades de Pointes
- Wide QRS tachycardia (diagnosis unknown)
- Electrical alternans
- Pacemaker or ICD
- Idioventricular rhythm – heart rate < 100 bpm
- Mobitz type II second degree or third degree atrioventricular (AV) block.
- AV dissociation
- Bifascicular Block (RBBB plus LAHB or RBBB plus LPHB)
- Left bundle branch block
- Wolff Parkinson White Syndrome
- Brugada Syndrome pattern
- QTcF ≥ 480 msec when RBBB is present
- Patients without complete right bundle branch block: QTc(F) ≥ 450 msec or an ECG that is unsuitable for QT measurements (e.g. poorly defined termination of the T wave).

11.5 Appendix 5: ECG Withdrawal Criteria

All ECGs conducted or overread after a patient has been randomized will be subject to ECG Withdrawal Criteria (including the pre-dose ECGs at Visit 1 and subsequent visits). A patient may be withdrawn from study medication if the 12-lead ECG recording during the study shows any of the following abnormalities:

The Investigator may withdraw patients from study treatment for any other clinically significant finding (Section 7.0). Triplicate ECGs (over a brief period of time) should be performed on patients experiencing any of the following or a clinically significant abnormality on their ECG per the Investigator's discretion, in order to confirm the abnormality in 2 of 3 measurements. The decision to withdraw a patient should also take into consideration the patient's medical history and prior/baseline ECGs.

- Sinus tachycardia ≥ 120 bpm (Sinus tachycardia ≥ 120 bpm should be confirmed by 2 additional readings at least 5 minutes apart).
- Sinus bradycardia < 37 bpm (Sinus bradycardia < 37 bpm should be confirmed by 2 additional readings at least 5 minutes apart).
- Increase in heart rate ≥ 40 bpm relative to baseline.
- Multifocal atrial tachycardia
- Supraventricular tachycardia (> 100 bpm)
- Atrial fibrillation with rapid ventricular response (rate > 120 bpm).
- Atrial flutter with rapid ventricular response (rate > 120 bpm).
- Ventricular tachycardia (non-sustained, sustained, polymorphic or monomorphic)
- Ventricular flutter
- Ventricular fibrillation
- Torsades de Pointes
- Evidence of Mobitz type II second degree or third degree atrioventricular (AV) block.
- AV dissociation
- 2:1 AV block
- Bifascicular Block (RBBB plus LAHB or RBBB plus LPHB)
- An increase in QTcF > 60 msec from baseline ECG
- Uncorrected QT > 600 msec
- For patients with QRS duration < 120 msec: QTc(F) ≥ 500 msec or an ECG that is unsuitable for QT measurements (e.g. poor defined termination of the T wave).
- For patients with QRS duration ≥ 120 msec: QTc(F) ≥ 530 msec or an ECG that is unsuitable for QT measurements (e.g. poor defined termination of the T wave).
- Myocardial infarction (acute or recent) Note: Evidence of an old resolved Myocardial infarction is not exclusionary.

11.6 Appendix 6: Guidelines for Identifying COPD Exacerbation

11.6.1 COPD Exacerbation Signs and Symptoms

The following are signs and symptoms of an exacerbation of COPD (Anthonisen, 1987):

Worsening of two or more of the following major symptoms for at least two consecutive days:

- Dyspnea
- Sputum volume
- Sputum purulence (color)

OR

Worsening of any one major symptom together with any one of the following minor symptoms for at least two consecutive days:

- Sore throat
- Colds (nasal discharge and/or nasal congestion)
- Fever (oral temperature >37.5 °C) without other cause
- Increased cough
- Increased wheeze

Patients experiencing worsening COPD symptoms for greater than 24 hours should:

- Contact the Investigator/study site immediately if they feel they need medical assistance.
- If the patient is unable to contact the Investigator/ study site, they should contact their primary care physician (or other health care practitioner as required) and contact the study site as soon as possible.
- Continue to record their symptoms and rescue albuterol/salbutamol use in their eDiary.
- If the patient seeks emergency/acute care for worsening respiratory symptoms, he/she should request the Health Care Provider (HCP) to contact the Investigator as soon as possible.

11.6.2 COPD Symptom Verification

Each exacerbation event will be verified with symptoms as defined in Section 11.6.1 and these symptoms will be documented in the case report form as part of the exacerbation assessment.

11.6.3 COPD Exacerbation Severity:

The definition of COPD exacerbation severity is as follows:

11.6.3.1 Moderate

A moderate exacerbation is defined as worsening symptoms of COPD *requiring a minimum of three days of treatment* with oral/systemic corticosteroids and/or antibiotics.

11.6.3.2 Severe

A severe exacerbation is defined as worsening symptoms of COPD requiring in-patient hospitalization.

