3.2.3 Other Endpoints

- Moderate/severe COPD exacerbation frequency over 24 Weeks (this individual study and pooled with data from study RPL554-CO-301).
- Time to first moderate/severe COPD exacerbation over 24 Weeks (this individual study and pooled with data from study RPL554-CO-301).
- Study withdrawal before 24 Weeks.
- EuroQol-5-Domain Questionnaire (EQ-5D-5L) at Week 12 (change from baseline).
- Healthcare Resource Utilization (HRU) over 24 Weeks.
- Average FEV₁ AUC_{6-12h} post-dose at Week 12 (change from baseline).
- Ensifentrine concentrations (sparse sample collection) at Weeks 6, 12, and 24.
- Patient genotype/phenotype including but not limited to cytochrome P-450 (CYP)2C9 and CYP2D6 metabolic activity.
- Interleukin (IL)-6, IL-8, and C-reactive protein at Weeks 12 and 24.

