16.3.1. OTHER EFFICACY VARIABLES & DERIVATIONS

16.3.1.1. COPD exacerbation

COPD exacerbations are collected on the “COPD Exacerbation” page of the eCRF and severity will be derived separately using data collected in the eCRF and as per the criteria specified in section 11.6.1. of the study protocol.

Site must enter at least 2 major symptoms, or one major symptom and one minor symptom AND meet the severity criteria below, considered as a moderate or severe exacerbation of COPD.

The severity of the COPD exacerbation will be calculated as per the following:

Moderate: Worsening symptoms of COPD requiring a minimum of three days of treatment with oral/systemic corticosteroids and/ or antibiotics.

Severe: Worsening symptoms of COPD requiring in-patient hospitalization.

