16.3.3. ANALYSIS OF OTHER EFFICACY VARIABLES

Change from baseline to average FEV₁ AUC_{6-12h} will be analyzed using ANCOVA approach and missing data will be imputed using imputation, as described in sections 16.1.3 and 16.2.2.1 of the SAP, respectively.

[figure not shown]
Model assumptions will be tested and solved, if failed, as per section 16.1.3 of the SAP.

The number of moderate or severe COPD exacerbations will be analyzed using a negative binomial model adjusting for treatment, region, actual background medication strata and actual smoking strata, as well as using log study time (years) as an offset. For study time, Visit 5 will be taken into account for completer patients, and End of Study visit or last contact date for withdrawal patients. The treatment difference from the negative binomial model will be expressed as an annualized risk ratio. The data will also be summarized by treatment group over duration of the study period.

Time to first moderate or severe COPD exacerbation during the study period will be presented as per following:

- Primary approach: Analyzed using the log-rank test, stratified by region, actual background medication strata and actual smoking strata. Summary of number of patients with events and number of patients censored will be summarized. Outcome visualized using a Kaplan-Meier plot.
- Sensitivity analysis: Analyzed using Cox proportional hazards Regression model stratified by region, background medication strata and smoking strata. Patients without exacerbations will be censored at last day in the treatment period, including period of recording after possible treatment withdrawal. The treatment difference in the Cox model will be expressed as a hazard ratio.

Testing proportional hazard assumptions:

1. Check that the covariates are independent of each other through proc phreg in SAS software.
2. Check that the hazard (hazard ratio) is independent of time through $\log(-\log(\text{survival}))$ vs $\log(\text{time})$ plot and an interaction test for treatment times $\log(\text{time})$.

The health index and VAS score for EQ-5D-5L questionnaire will be analyzed using ANCOVA approach, as described in section 16.1.3 of the SAP, with data imputation described in section 16.2.2.3 of the SAP.

HRU over 24 weeks will be summarized for each event and for overall count.

Analysis for the genetics data is described in section 18 of the SAP.

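### A first COPD exacerbation that is fatal before admission and before three days of treatment scores as no event, because neither severity criterion mentions death

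*Protocol*

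**What the plan says.** Protocol 11.6.3 recognises two severity classes. The moderate entry (11.6.3.1) opens "A moderate exacerbation is defined as worsening symptoms of COPD" and then requires at least three days of systemic corticosteroids and/or antibiotics. The severe entry (11.6.3.2) reads "A severe exacerbation is defined as worsening symptoms of COPD requiring in-patient hospitalization". Section 11.6.3.3 adds that an event that starts as moderate and becomes severe is captured as severe.

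SAP 16.3.1.1 derives severity from eCRF data with the same two criteria: "Worsening symptoms of COPD requiring a minimum of three days of treatment with oral/systemic corticosteroids and/ or antibiotics" for moderate and "Severe: Worsening symptoms of COPD requiring in-patient hospitalization". It first requires the major/minor symptom combination, and the event must then "AND meet the severity criteria below, considered as a moderate or severe exacerbation of COPD". Both conditions have to hold.

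Frequency and "Time to first moderate/severe COPD exacerbation over 24 Weeks" are listed in Protocol 3.2.3, for this study and pooled with CO-301. SAP 16.3.3 analyses the count with a negative binomial model and a log study-time offset, and the time to first event with a stratified log-rank test and a Cox model. On censoring it says "Patients without exacerbations will be censored at last day in the treatment period, including period of recording after possible treatment withdrawal". Protocol 9.4.1 has the same rule. Neither document gives a rule for death in these analyses, and the estimand table in SAP 2.5 does not cover exacerbations.

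**The concern.** Death is the worst outcome an exacerbation can have, yet it is not a severity criterion. A patient who dies of a first exacerbation at home or in transit, before being admitted and before completing three days of treatment, satisfies neither class. The analysis then treats that patient as someone who had no exacerbation, and the follow-up ends because of the very event being studied. Such censoring is informative.

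What is at stake is the exacerbation rate ratio and hazard ratio in this study. The same individual patient data also feed the pooled analysis with CO-301, although that analysis has its own SAP, which is not among these documents.

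**Working it through.** **1. The plan's own figures.** No exacerbation rate, event count, death rate or power is stated for these endpoints. The only powered figure is for the primary endpoint (Protocol 9.2): SD 250 mL, difference 59 mL, 500 vs. 300 patients, two-sided 5%, stated power 90%. Recomputed, the power is 89.8%, so it reproduces. It does not depend on the point made here.

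**2. Following a fatal exacerbation through the rules.**

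| Patient who dies of an exacerbation without admission | Moderate criterion | Severe criterion as written | Negative binomial | Time to first event |
|---|---|---|---|---|
| No earlier event, under three days of treatment | Not met | Not met | 0 events | Censored by default |
| No earlier event, three or more days of treatment | Met | Not met | 1 event, graded moderate | Event |
| Earlier qualifying event, fatal one under three days of treatment | Not met for the fatal one | Not met | Fatal one not counted | Already an event |

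Only the first row loses the patient as an event altogether. The second row loses the grade, which sits badly with the intention of 11.6.3.3 that escalating events be captured as severe.

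**3. A second test that a rapid death can fail.** Protocol 11.6.1 requires symptom worsening on at least two consecutive days, and 11.6.2 requires each event to be verified against that and documented. Adding death to the severity wording would not by itself rescue a death within the first day or two.

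**4. Whether the death is recorded elsewhere.** Protocol 8.7.7 and 11.6.6 record an exacerbation as an AE only when it meets the SAE definition. Protocol 11.7 says that an event that is not an AE cannot be an SAE even when serious criteria are met, and gives death from disease progression as an example. An investigator could follow either text, so the passages need to be reconciled.

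**5. Size as a share of events.** All inputs except the 800 patients and 24 weeks are assumptions.

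- Exposure: 800 × 24/52 = 369 patient-years.
- Assumed 0.3 to 0.8 moderate/severe events per patient-year: 369 × 0.3 = 111 and 369 × 0.8 = 295 events.
- Assumed 1 to 4 uncaptured fatal events: 1/295 = 0.3% and 4/111 = 3.6%.

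**6. Size as a share of first events.** With E captured first events and D uncaptured fatal ones, the share is D/(E + D).

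| Assumed patients with a first event | E | D = 1 | D = 5 |
|---|---|---|---|
| 5% of 800 | 40 | 2.4% | 11.1% |
| 10% of 800 | 80 | 1.2% | 5.9% |
| 20% of 800 | 160 | 0.6% | 3.0% |

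**7. Effect on the treatment comparison.** Assume 10% captured first events in each arm (50/500 and 30/300, risk ratio 1.00) and, as an extreme, five uncaptured deaths all in one arm.

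- All on ensifentrine: (55/500)/(30/300) = 0.110/0.100 = 1.10. The plan would report 1.00, which flatters ensifentrine.
- All on placebo: (50/500)/(35/300) = 0.100/0.117 = 0.86. The plan would report 1.00, which is conservative for ensifentrine.
- Deaths in proportion to 5:3: the ratio barely moves.

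**The case against.** **The wording may already cover these patients.** Both definitions say requiring, not receiving. An exacerbation severe enough to kill can be read as one that needed admission. The SAE definition in Protocol 11.7 also describes hospitalisation as detention in a hospital or emergency ward, so an emergency-department death is not clearly excluded. This stands as an ambiguity. The documents do not settle it, and because SAP 16.3.1.1 derives severity from eCRF data, the derivation needs an explicit rule.

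**Many fatal cases are counted.** A reader might infer that every patient who dies of an exacerbation before admission scores as event-free. The documents do not support that: the endpoint is the moderate/severe composite, three days of treatment is enough without admission, and an earlier qualifying event already counts in the time-to-first analysis.

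**The deaths are not concealed.** A reader might infer that an imbalance in such deaths would be hidden. SAP 17.1, 17.1.3 and 17.1.4 tabulate serious TEAEs and TEAEs with a fatal outcome by system organ class and preferred term, with serious TEAEs shown by treatment group. This stands, provided the death is recorded as an SAE, which step 4 shows is not assured.

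**The direction is not fixed.** A reader might infer that the error always favours ensifentrine. Step 7 shows that it favours whichever arm has more such deaths.

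**The stakes are low.** The endpoints are listed under other endpoints and are absent from the test order in Protocol 9.1 and SAP 7.4. The trial lasts 24 weeks and excludes life-threatening COPD, recent COPD hospitalisation and recent steroid-treated exacerbations (Protocol 5.2). Nothing in the documents shows that even one such death is expected. All of this stands. It limits the size of the problem but does not supply the missing rule.

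**Conclusion.** The point holds in a narrow form. As written, a patient with no earlier qualifying exacerbation who dies of one before in-patient admission and before three days of steroid or antibiotic treatment has no moderate/severe event. That patient adds nothing to the negative binomial count and is censored in the log-rank and Cox analyses. The censoring follows by default from the general rule; neither document states it for deaths. A patient treated for three days who dies unadmitted is kept but under-graded.

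The number affected is unknown and probably very small. The range of 0.3 to 3.6% of moderate/severe events, and the shares of first events in step 6, rest wholly on assumed event and death rates. A larger percentage could be produced by dividing by severe events alone, but severe events are not a separate endpoint in Protocol 3.2.3 and the documents give no severe share. The primary endpoint, key secondary endpoints, alpha and sample size are untouched.

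The change is still worth making: the rule gives a wrong result for the worst outcome, and correcting it is cheap.

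**What to change.** Four linked changes:

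1. In Protocol 11.6.3.2 and SAP 16.3.1.1, for endpoint purposes, add *or resulting in death* after the hospitalisation criterion.
2. In SAP 16.3.1.1, state that a death attributed to a COPD exacerbation counts as a severe event at its onset date even when the two-consecutive-day symptom test cannot be documented. Identify such cases from the exacerbation form together with fatal SAE records.
3. In SAP 16.3.3, state that other deaths are censored at the date of death.
4. Reconcile Protocol 8.7.7 and 11.6.6 with the SAE definition in 11.7, so that a fatal exacerbation is always recorded. Change 2 depends on this.

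The cost is a phrase in each document, two sentences in the SAP, one reconciliation in the protocol and a merge of two data sources. The change concerns endpoint definition and recording only; the treatment-discontinuation rule in Protocol 11.6.7 names hospitalisation in its own words and need not change. The downside is that attribution of a few deaths to COPD rests on the investigator's report, without the symptom verification applied to other events.
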